Accommodative Relief for Uncomfortable Non-Presbyopes

Study Protocol Including Statistical Analysis Plan

NCT03544216

Date of Document: 11/21/2017

Accommodative Relief for Uncomfortable Non-Presbyopes

Principle Investigator: [name], OD, PhD

Co-Investigators: [name], OD, MS and [name]

I. Objective

To determine how multifocal contact lenses affect contact lens comfort in non-presbyopic contact lens wearers.

II. Background and Rationale

Contact lens discomfort is a condition characterized by episodic or persistent adverse ocular sensations related to lens wear, either with or without visual disturbance, resulting from reduced compatibility between the contact lens and the ocular environment, which can lead to decreased wearing time and discontinuation of contact lens wear.¹ Patients with contact lens discomfort typically reports symptoms such as dryness, irritation, discomfort, and fatigue.¹ With today's growing use of digital devices, visual, ocular, and musculoskeletal (neck and shoulder pain) symptoms have been reported to include eye strain, eye fatigue, burning and irritation of the eyes, tired eyes, dry eyes, ached in and around the eyes, blurred vision at near, blurred vision when looking from near to far, headache, neck ache, and shoulder pain.² For contact lens wearers, prolonged use of digital devices and the decreased blink rate associated with such activities, have been suggested causes of contact lens discomfort.^{3, 4} Despite the etiology, severity of dry eye clinical signs rarely correlates with severity of discomfort symptoms.⁵ Because of this, treatments are focused on symptom relief alone.

Interestingly, uncomfortable contact lens wearers report symptoms very similar to patients with insufficient accommodation. Accommodation is the physiological ocular response that allows us to focus at near.⁶ Similar to subjects with contact lens discomfort, patients with insufficient accommodation report symptoms like sore eyes, tired eyes, and symptoms that increase and become more intense at the end of the day.^{7, 8} In a group of young, uncomfortable contact lens wearers, our laboratory found that accommodative insufficiency was unusually high and more prevalent than previously reported in the normal population.⁹

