Subjective Refractive Error Determination: Subjects who meet all inclusion criteria for the study will be enrolled and be fitted in two different kinds of contact lenses throughout the course of the study. Before fitting the contact lenses, a subjective refraction will be performed to determine the best correction and contact lens power for the subject. The refraction will be performed by a licensed, trained optometrist ([name]) using a phoropter. Patient responses will be used to determine the final refractive error. This method is identical to refractive error determination in a regular eye exam.

Contact Lens Fitting: In this crossover trial, single vision Bausch + Lomb ULTRA® contact lenses and Bausch + Lomb ULTRA® for Presbyopia contact lenses will be fitted by a licensed optometrist. Bausch + Lomb ULTRA® and Bausch + Lomb ULTRA® for Presbyopia are FDA-approved daily wear soft contact lenses. All subjects will be habitual soft contact lens wearers, so no increased risk will be assumed by fitting the Bausch + Lomb ULTRA® contact lenses.

Anterior Ocular Segment Assessment: While the risk of contact lens complications (ocular inflammation, infection, etc.) in this study is extremely low, the anterior segment ocular health of both eyes of every subject will be assessed by a licensed optometrist at each visit to ensure no complications have occurred. This assessment will also include the ocular adnexa (lid margin and Meibomian glands). In the unlikely event that a complication does occur, the subject will be treated by a licensed optometrist and dismissed from the study.

c. Detailed Study Procedures

Overview

This randomized, prospective, crossover clinical trial will recruit uncomfortable, single vision, soft contact lens wearers in the non-presbyopic age range. The tenants of the Declaration of Helsinki will be followed. Complete inclusion criteria are listed in Table 1. Each subject will receive a single vision (Bausch + Lomb ULTRA®) and multifocal contact lens (Bausch + Lomb ULTRA® for Presbyopia) to wear for 2 weeks each. Subjects will be masked and randomly assigned to the first lens and then they will be crossed over to the remaining lens for the second 2-week period. Figure 1 displays a flow chart of the planned study procedures.

Subject Enrollment and Baseline Examination and Fitting

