Pre-presbyopes with symptoms of contact lens discomfort and asthenopia will be recruited from The Ohio State University College of Optometry Clinics. Interested subjects will be instructed to contact investigators by email. The Contact Lens Dry Eye Questionnaire-8 (CLDEQ-8), a survey validated to reflect change in opinion of contact lenses,¹¹ will be administered over the phone to ensure each subject has significant discomfort symptoms. Each subject must have a score of ≥ 12 points¹⁵ to qualify for the first, baseline examination.

At the baseline examination, inclusion criteria will be confirmed. The presence of concurrent dry eye or a binocular vision disorder (a group of disorders that involved how the eyes move together) will confound study results, so subjects with significant signs of these conditions will be excluded from the study (as defined in Table 1). With the each subject's habitual contact lens correction, heterophoria at distance and near and NPC will be measured to determine binocular vision eligibility. Accommodative function will also be assessed at this time. TBUT, ocular surface staining, and Schirmer testing will be performed to determine dry eye eligibility. Keratograph 5M tear imaging will also be performed at this time. A general anterior segment assessment will be made and assessment of the lid margins and Meibomian glands after habitual lens wear will be recorded. The CISS will be administered at the baseline examination. Subjects who meet all inclusion criteria will be enrolled and randomized (blocked randomization design with a 1:1 allocation ratio) to receive either the single vision Bausch + Lomb ULTRA® or single vision Bausch + Lomb ULTRA® for Presbyopia contact lenses first. All subjects who complete the baseline examination (whether enrolled or not) will receive \$40 cash and a parking pass.

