Subjects will be asked which of the two trial lens pairs they preferred and be asked which lens (single vision or multifocal) they think they had first and second. After all testing and procedures have been completed, subjects will be instructed to return to habitual contact lens wear and informed of what lenses they had during the first and second trial periods. Subjects will receive \$40 cash and a parking pass at the end of the third examination.

Data Analysis and Sample Size Justification

Paired *t* tests will be performed to compare mean CLDEQ-8 scores with habitual single vision lenses, single vision Bausch + Lomb ULTRA® contact lenses, or Bausch + Lomb ULTRA® for Presbyopia contact lenses to one another. Repeated measures ANOVA testing will be performed to determine if contact lens comfort (CLDEQ-8 score) is affected by age or magnitude of myopia when subjects are corrected with their habitual single vision lenses, single vision Bausch + Lomb ULTRA® contact lenses, or ULTRA® for Presbyopia contact lenses. CISS scores throughout the trial will be analyzed in the same way as the CLDEQ-8 scores. To determine if accommodative ability is related to multifocal preference, paired *t* tests will be used to compare contact lens preference (single vision versus multifocal) to initial accommodative function (lag/lead) values.

In order to detect a conservative standardized effect size of 0.6 ($\alpha = 0.05$, $\beta = 0.20$), a sample size of 45 subjects would be necessary. A previous cross-over trial utilizing the CLDEQ-8 reported a 20% loss-to-follow-up rate.¹¹ Anticipating and accounting for a similar rate in our subject enrollment, a sample of 54 subjects would be appropriate. Because the hypotheses of this study have never been tested, we recognize that this initial sample size may seem inadequate after all data is collected. So, our initial 54-subject sample size will be increased by an additional 25% to allow for additional data collection that may be necessary. Therefore, 68 subjects (34 subjects per group) will be sought for IRB approval to account for the possibility of needing more subject data to make reliable study conclusions.

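### Three lens comparisons on each of two scores, with no primary contrast named: the single 0.05 in the sample size is not what the tests deliver, and an unrandomised comparison could carry the conclusion

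*Combined protocol and SAP*

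**What the plan says.** The Objective is "To determine how multifocal contact lenses affect contact lens comfort in non-presbyopic contact lens wearers"; it names no comparator lens.

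Under Data Analysis and Sample Size Justification, the method for CLDEQ-8 is the paired t test, and the text reads "tests will be performed to compare mean CLDEQ-8 scores with habitual single vision lenses, single vision Bausch + Lomb ULTRA® contact lenses". The multifocal ULTRA lens is listed as the third condition, and every lens is to be compared with every other. The next score follows suit: "CISS scores throughout the trial will be analyzed in the same way as the CLDEQ-8 scores". CISS with habitual lenses is available, because "The CISS will be administered at the baseline examination", so all three pairs can be tested on both scores. Repeated measures ANOVA is added for age and myopia, and further tests relate lens preference to accommodative lag or lead.

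The sample size paragraph begins "In order to detect a conservative standardized effect size of 0.6" and arrives at 45 subjects with alpha 0.05 and power 0.80. It attaches no score and no lens pair to these figures, and 0.05 appears nowhere else as a test level.

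On allocation, the Overview says "Subjects will be masked and randomly assigned to the first lens". Only the order of the two study lenses is randomised. The habitual lens is always the pre-study condition. The only CLDEQ-8 described for it is the telephone screening score, which had to be 12 or more.

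**The concern.** There are two separate problems.

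The first is the error rate. A trial sized on one test at 0.05 will run three tests on its comfort score and three on a second score, and nothing says which result answers the objective. The chance of some false finding is then well above 0.05.

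The second is which contrast may carry the claim. Multifocal versus single vision ULTRA is randomised, masked to the subject, and isolates the multifocal optics. Multifocal versus habitual is none of these. On CLDEQ-8 it also compares a score selected for being high with a later, unselected one. Nothing in the plan stops a drop from the habitual score being reported as a multifocal benefit when the randomised contrast shows none.

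**Working it through.** **Inputs from the documents.** Standardised effect 0.6, alpha 0.05, power 0.80, N = 45, 20% loss; three lens conditions; two scores; CLDEQ-8 entry threshold 12.

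**Assumed, because the documents do not give them.** Two-sided tests; CLDEQ-8/CISS correlation from 0 to 0.9; equal correlations between lens conditions; for the selection illustration, CLDEQ-8 SD 5, unselected mean 12 to 16 and retest correlation 0.5 to 0.8.

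**1. The plan's own figure.**
- Two-sample t test, d = 0.6, two-sided 0.05, power 0.80: 44.6, so 45 per group.
- Paired t test with 0.6 on the between-subject SD and zero correlation: 45.6, so 46.
- Paired t test with 0.6 on the SD of the differences: 23.8, so 24.
- Inflation: 45 × 1.20 = 54, and 54 × 1.25 = 67.5, so 68, as stated.

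The 45 is therefore recovered as a single test at 0.05.

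**2. Number of tests.** Three lens conditions give 3 pairs, and 3 pairs × 2 scores = 6 tests. Four include the multifocal lens (two against single vision ULTRA, two against habitual). Four include the habitual lens. Two (habitual versus single vision ULTRA) include no multifocal lens.

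**3. Chance of at least one false positive, either direction, no true lens differences.** Simulated paired t tests at two-sided 0.05. The sample sizes were 45, and 67 completers: (69 − 15) enrolled before the new recruitment round, plus 30 = 84, and 84 × 0.8 = 67. Sample size makes almost no difference.

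| Family | CLDEQ-8/CISS correlation | Rate |
|---|---|---|
| 3 tests, CLDEQ-8 only | not applicable | 0.12 |
| 6 tests | 0.9 | 0.17 |
| 6 tests | 0.7 | 0.20 |
| 6 tests | 0.5 | 0.21 to 0.22 |
| 6 tests | 0 | 0.23 |

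For reference, independent tests would give 1 − 0.95³ = 0.143 and 1 − 0.95⁶ = 0.265. With markedly unequal correlations between lenses, the three-test rate is about 0.11 to 0.12, and the six-test rate at zero correlation between the scores is about 0.21 to 0.22.

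**4. The narrower risk: a false result that favours the multifocal.** Counting only tests that include the multifocal lens, and only the favourable direction, the rate is about 4% to 5% over the two CLDEQ-8 tests. It is about 6% to 9% over the four tests on both scores. Both figures are before any selection effect.

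**5. The selection effect.** With mean μ, SD s and retest correlation ρ, and no lens effect, the expected fall from the selected habitual score is (1 − ρ) × s × λ, where λ = φ(a)/(1 − Φ(a)) and a = (12 − μ)/s.
- μ = 16, ρ = 0.8: λ = 0.368; 0.2 × 5 × 0.368 = 0.37 points.
- μ = 14, ρ = 0.7: λ = 0.562; 0.3 × 5 × 0.562 = 0.84 points.
- μ = 12, ρ = 0.5: λ = 0.798; 0.5 × 5 × 0.798 = 1.99 points.

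Simulated over this range, each habitual-lens CLDEQ-8 test is significant in about 13% to 82% of null trials at n = 45 and about 16% to 94% at n = 67. The randomised contrast stays near 5%. More subjects make the habitual-lens problem worse.

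**The case against.** The strongest reply is that CLDEQ-8 is plainly the main score. The objective is comfort, the analysis section equates comfort with CLDEQ-8, and the 8/14/2017 extension rests on a CLDEQ-8 result. CISS gets one derivative sentence. That is a fair reading, and under it the family is three tests at about 0.12. It does not settle which lens pair decides. The ANOVA does not act as a gate either: it is assigned to age and myopia, and the t tests are not conditional on it.

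The randomised contrast is already planned, and its own test has a 5% error rate. That stands, and it limits the severity.

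Four stronger readings are tempting and are not supported.
- A reader might infer that any of the six tests could be reported as a multifocal benefit. Two contain no multifocal lens.
- A reader might take 0.17 to 0.23 as the risk of a false multifocal claim. It counts any lens and either direction; the narrower risk is in step 4. The upper end also needs uncorrelated scores, which is unlikely because the CISS paragraph describes the symptoms as similar.
- A reader might say the plan gives all six tests equal standing at 0.05. It is silent on this, and it defines no success criterion. The point is only that nothing prevents such a claim.
- A reader might add the age, myopia and preference tests to reach a larger figure. Their number and dependence are not specified, and they address other questions.

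**Conclusion.** The point holds and should be fixed. One alpha of 0.05 underlies the sample size, but the planned tests give about 0.12 over the CLDEQ-8 pairs and about 0.17 to 0.23 over both scores. The three-test figure rests on near-equal correlations between lenses; the six-test range also rests on the assumed correlation between the scores.

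The more serious part is that the unrandomised multifocal-versus-habitual contrast is left free to support the conclusion. The direction of that bias follows from the entry threshold. Its size depends on an SD, mean and retest correlation that the documents do not give, so the percentages in step 5 are illustrative. They apply to CLDEQ-8 and to the telephone score used as the habitual value; a fresh score at the baseline examination would reduce the effect, but none is described.

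**What to change.** Amend the Data Analysis and Sample Size Justification section as follows.

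1. Primary test: CLDEQ-8, ULTRA for Presbyopia versus single vision ULTRA, two-sided 0.05. Any conclusion that multifocal lenses change comfort rests on this test.
2. Secondary: the same contrast on CISS, tested at 0.05 only if the primary is significant.
3. Habitual-lens contrasts: estimates with 95% confidence intervals, supporting no efficacy claim.
4. Age, myopia and preference tests: labelled exploratory.
5. Date the amendment. State that completers' data had been analysed by 8/14/2017 and that the age interaction (p = 0.12) led to the 30 added subjects. A hierarchy set after that look is not fully prospective, and readers should be told so.

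**Cost.** No extra subjects, and no loss of power on the main contrast. CISS cannot be claimed if CLDEQ-8 fails, and the habitual-lens contrasts become descriptive. The alternative, equal standing with Bonferroni, would raise the 45 to about 60 to 62 for three tests or 70 to 71 for six. If 0.6 refers to the SD of the paired differences, the needs are 32 and 38 against 24 for one test. The plan should state which SD is meant.

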NPC: NPC is a routine clinical measurement that assesses the ability of the eyes to converge and accommodate while viewing a near target.¹⁴ NPC will be evaluated binocularly with the subject's habitual correction using a push-up technique. An accommodative target (20/30 near letter) on a fixation stick will be slowly moved closer towards the subject's central visual axis until the subject experiences constant diplopia. The distance from the bridge of the subject's nose to this point will be recorded as the break point. Subjects with a break point of 6 cm or higher will be excluded from the study.

Accommodative Function: Accommodative function (lead/lag), or the ability of the subject to focus when reading, will be measured with an autorefractor. The autorefractor is a non-contact instrument that measures refractive error. Subjects will wear their habitual contact lens correction. Accommodative response will be measured at two stimulus levels with each pair of contact lenses (habitual, single vision, and multifocal) (2.00 and 4.00 diopters) to determine how accurately the subject focuses on letter visual targets at various distances while corrected with different contact lenses.

Dry Eye Testing: Subjects who have significant signs of dry eye will be excluded from the study. Basic dry eye testing, similar to that performed during a regular eye exam, will be performed to ensure subjects with dry eye do not confound study results. Tear break-up time (TBUT), ocular surface staining, and Schirmer test will be performed at the baseline examination. All dry eye tests will be performed on the right eye only.

TBUT: TBUT measurements are commonly used to assess severity of dry eye. The measurement quantifies the time it takes for the tear film to break-up on the ocular surface after a complete blink. To measure TBUT, fluorescein sodium will be instilled in the inferior palpebral conjunctiva using with a Barnes-Hind Ful-Glo Fluorescein Sodium Ophthalmic Strip that has been wetted with a drop of non-preserved saline. After instillation, the subject will be placed in a slit lamp and

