Updated sample size (03/07/2017): At this point in the study, we have seen 26 total subjects: 17 were successfully enrolled and 9 failed to qualify for the study (did not meet all dry eye and binocular vision inclusion criteria) after completing the baseline examination. Therefore, approximately 35% of the subjects who have participated in baseline examinations have failed. With 17 subjects enrolled, we need to recruit and enroll an additional 51 subjects to complete the study. Considering our recent experience with enrollment, we will assume that 35% of these 51 baseline examinations (or about 18) will not qualify for the study. Therefore, we are requesting to increase our original sample size of 68 subjects by 18 and recruit a sample size of 86 (43 subjects per group).

Updated sample size (8/14/2017): Upon initial data analysis of the subjects who have completed the study, we found an interaction between subject age group and change in CLDEQ-8 survey score that, while not statistically significant ($p = 0.12$), was clinically significant (an approximate 4-point difference between age groups) according to CLDEQ-8 interpretation. We have hypothesized that this clinically relevant finding may have lacked statistical significance because of an inadequate sample size. Because of the lack of software or well-developed methods for calculating the sample size for an interaction in a cross-over study, a simulation study was conducted to estimate what a sufficient sample size would be. The simulation assessed adding more subjects to the sample – using

the subjects currently in the sample. This iterative process was conducted to draw 10 different samples from which sample size was estimated in order to attempt to replicate the original finding with greater power. Given the simulation, it was recommended that 30 additional subjects be tested. At this point, approximately 27% of subjects who present for the baseline examination fail to qualify for the study, so we will increase the 30 additional subjects by 27% (8 subjects) and, therefore, increase our overall sample size by 38 subjects. In conclusion, the new number of recruited participants will increased from 86 to 124.

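### The tests of age, myopia and lag/lead carry no adjustment, order or exploratory label, and the age test was singled out after the data had been seen

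*Combined protocol and SAP*

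**What the plan says.** The section Data Analysis and Sample Size Justification first plans paired t tests between lenses. It then turns to who benefits:

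- **Age and myopia on CLDEQ-8.** "Repeated measures ANOVA testing will be performed to determine if contact lens comfort (CLDEQ-8 score) is affected by age or magnitude of myopia", across the habitual, single vision study and multifocal lenses.
- **The same on CISS.** "CISS scores throughout the trial will be analyzed in the same way as the CLDEQ-8 scores".
- **Lag/lead against preference.** Preference for single vision or multifocal is compared with initial accommodative lag/lead values. Under Measurement/Instrumentation, Accommodative Function, "Accommodative response will be measured at two stimulus levels with each pair of contact lenses", at 2.00 D and 4.00 D.

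An alpha of 0.05 appears once, in the sample-size sentence that begins "In order to detect a conservative standardized effect size of 0.6". The document names no key modifier, testing order, adjustment or exploratory label.

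The sample-size update of 8/14/2017 reports on subjects who had completed by then: "we found an interaction between subject age group and change in CLDEQ-8 survey score that, while not statistically significant" (p = 0.12), with a difference of about 4 points between age groups. It puts the lack of significance down to sample size and adds 30 subjects.

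**The concern.** Each of these analyses is worded as a question to be settled. With several such tests at 0.05 and nothing said about which one counts, the trial could report that multifocal lenses suit older, more myopic or poorly accommodating wearers on the strength of whichever test crossed the line. Naming a primary lens comparison would not prevent this, because it governs the lens t tests and not these. Nor are the tests mere description in this trial: one modifier result has already led to an enlargement of the study.

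**Working it through.** **The plan's own figure.** The document gives no family-wise error rate. Its one figure tied to alpha is 45 subjects for a standardized effect of 0.6, alpha 0.05, power 80%. A two-sided two-sample t test needs 45 per group (power 80.4%); a one-sided normal approximation gives 35. So 45 fits a two-sided 0.05 spent on a single comparison of means. Applying that level to each modifier test is an inference.

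**Count of tests.** Two modifiers (age, myopia) × two scales (CLDEQ-8, CISS) = 4. Lag/lead against preference adds 1, or 2 if the two stimulus levels are tested separately.

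**Independent tests.** Chance of at least one false positive = 1 − 0.95^m:

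- m = 4: 1 − 0.8145 = 0.185
- m = 5: 1 − 0.7738 = 0.226
- m = 6: 1 − 0.7351 = 0.265

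**Correlated tests.** The document gives no correlations, so these are assumed. The four test statistics were simulated as multivariate normal, rejecting when |z| > 1.96. Lag/lead tests are taken as independent of the four. For five tests the rate is 1 − (1 − F4) × 0.95, where F4 is the four-test rate. For six it is 1 − (1 − F4)(1 − F2), where F2 is the rate for two lag/lead tests correlated 0.8 (0.078) or 0.5 (0.091).

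| CLDEQ-8/CISS correlation | Age/myopia correlation | Four tests | Five | Six |
|---|---|---|---|---|
| 0 | 0 | 0.185 | 0.226 | 0.249-0.259 |
| 0.5 | 0 | 0.173 | 0.215 | 0.238-0.248 |
| 0.8 | 0.5 | 0.139 | 0.182 | 0.207-0.218 |

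The four-test rate is therefore 0.139/0.05 = 2.8 to 0.185/0.05 = 3.7 times the nominal level. A regression simulation with 55 or 67 completers gave 0.153-0.175 for the four tests.

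**The age test after the August 2017 look.** A two-sided p = 0.12 corresponds to z₁ = 1.555. If the same contrast is tested again with those subjects pooled in, and there is no interaction, the chance that the final result is significant in the same direction is

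1 − Φ[(1.96 − √t · 1.555) / √(1 − t)],

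where t is the share of the final information already seen. The opposite direction adds almost nothing. The number in that analysis is not stated. The 11/21/2017 update implies 69 − 15 = 54 enrolled before the extension, so at most 54, and the target is 54 + 30 = 84.

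- t = 54/84 = 0.64: (1.96 − 0.802 × 1.555)/0.598 = 1.19, giving 0.116
- t = 0.50 (42 of 84, assumed): (1.96 − 0.707 × 1.555)/0.707 = 1.22, giving 0.112

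So the conditional false-positive chance is about 11-12%, not 5%.

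**The case against.** The best defence is that the focus is clear enough in practice. Comfort is the stated objective, CLDEQ-8 is an entry criterion and leads the analysis, and age by CLDEQ-8 drove the extension. Subgroup analyses of hypotheses never tested before are often read as exploratory without being labelled so. This reduces the practical ambiguity. It does not remove it, because nothing in the text stops a myopia, CISS or lag/lead result from being presented as established, and age gained its prominence only after data had been seen.

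Three limits on the count stand. The plan does not say whether the ANOVA term is a main effect or a lens-by-modifier interaction, or whether age and myopia share a model; only the 8/14/2017 update speaks of an interaction. Lag/lead against preference is an association with preference, not effect modification of a score. Both stimulus levels are measured, but the plan does not say that both are tested.

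Two stronger readings are tempting. A reader might infer that the chance of a false claim is simply about one in four. That needs six tests; the five-test range is 18-23%. A reader might also infer that naming age by CLDEQ-8 as the one confirmatory modifier would restore 5%. The update does not support this, since the test was chosen on interim data, and a Holm correction over the four tests would not account for that look.

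**Conclusion.** The omission is real and should be corrected. With no true relations, the chance of at least one false positive is about 14-18.5% for the four age and myopia tests, 18-23% with one lag/lead test and 21-26% with two. These figures rest on two-sided 0.05 per test, on the assumed correlations, and on lag/lead tests independent of the others. They leave out the pairwise lens comparisons, so they are not the error rate of the whole plan.

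The age by CLDEQ-8 test needs separate treatment. Pooled with the subjects already analysed, it has about an 11-12% chance of a false positive given the interim result, if 50-64% of the final information had been seen and the contrast is unchanged. The document does not show that a false claim was made. It shows that the plan sets no limit on one.

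**What to change.** Add to Data Analysis and Sample Size Justification:

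> Analyses of myopia on CLDEQ-8, of age and myopia on CISS, and of lag/lead (2.00 D and 4.00 D) against preference are exploratory. Estimates with 95% confidence intervals will be reported, and no claim will rest on their p values. The age by CLDEQ-8 interaction was singled out after an unplanned analysis in August 2017 (p = 0.12), so a test that pools those subjects is also exploratory. Any confirmatory claim about age will rest only on subjects not included in that analysis.

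Record which subjects were in the August 2017 analysis, so that the split can be made.

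Do not make the age test conditional on a significant overall multifocal versus single vision difference. An age interaction matters most when the overall effect is diluted, and such a gate would block it there.

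**Cost.** No new data, visits or subjects are needed. An isolated p < 0.05 for a modifier can no longer be reported as confirmed, and a confirmatory age test on later subjects has less power. As an illustration, suppose the interim difference is the true one, the precision is that implied by p = 0.12, and all 84 subjects complete. The expected z is then 1.555 × √(n/n₁), where n₁ is the number in the August 2017 analysis.

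- n₁ = 54: 30 later subjects give 1.16 (power about 21%); all 84 give 1.94 (about 49%).
- n₁ = 42: 42 later subjects give 1.555 (about 34%); all 84 give 2.20 (about 59%).

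The sponsor should accept that loss openly or report the age result as exploratory.
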